Measures. Data will be collected through a combination of self-report, medical records abstraction, and UDS. In general, the baseline survey will assess past year or lifetime while the follow-up assessments will assess the period since the last assessment. For self-report data, questionnaires with established reliability and validity will be used whenever possible. Reviews suggest that self-report drug use data has a moderate to strong degree of reliability and validity.⁸⁰ The accuracy of self-reported information on substance use is enhanced when confidentiality is ensured and the interview is administered when the respondent is not intoxicated.⁸¹ The voluntary UDS will be used to improve the validity of self-reported substance use.

Measure title	Baseline	Post-Intervention	Follow-ups
Current Opiate Misuse Measure (COMM)	X		X
Overdose Risk Behaviors (ORB)	X		X
Overdose Experiences, Self –Alcohol (OESWA)	X		X
Overdose Experiences, Self and Witnessed – Drugs (OESWD)	X		X
Treatment Service Review (TSR)	X		X
Alternative Therapies (AT)	X		X
Revised Injury Behavior Checklist (RIBC)	X		X
Pain Treatment Satisfaction Scale (PTSS)	X		X
Safe Storage and Disposal of OAs	X		X
Veterans RAND 12-Item Health Survey (VR-12)	X		X
Knowledge of Overdose Risk Factors (OK)	X	X	X
Overdose Education and Naloxone Distribution (OEND)	X		X

Behavioral Intentions (BI)	X	X	X
Self-Efficacy-Overdose Self (SEOS)	X	X	X
Perceived Satisfaction and Utility (PSU – I & PSU – C)		X	
National Comorbidity Survey (NCS)	X		X
Brief Pain Inventory – Short Form (BPI)	X		X
Pain, Enjoyment and General Activity Scale (PEG)	X		X
Centrality of Pain Scale (CPS)	X		X
Addiction Severity Index (ASI)	X		X
Alcohol, Smoking and Substance Involvement Treatment (ASSIST)	X		X
Demographic information	X	X	X
Military service information (MSI) not individually labeled but included in Demographics	X		X

Outcomes. (Measured at Baseline and Follow-up, except where noted)

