OAs Prescribed. We will determine prescribed OA regimen from pharmacy data using established methods¹² with standard morphine equivalency ratios.¹¹ The Medication Possession Ratio (MPR)⁸² will also be used to measure actual medication use/adherence by accounting for early and late refills. The MPR can identify patients who consistently refill early, an indication of overuse. OA therapy outside of VHA will be assessed and those participants who report being prescribed OAs by non-VHA care providers will be asked about formulation, dose, and prescribed schedule, and the dose and MPR will be adjusted accordingly. Pharmacy data will also be used to determine prescribed dose for the eligibility criteria of 20 MEM/day.

Aberrant OA Use. The Current Opiate Misuse Measure (COMM) is a 8-item self-report of recent aberrant use developed for, and validated in, patients receiving OAs.⁶⁵ Items include: getting medications from someone other than the prescribing physician, taking medications differently than prescribed, and taking for reasons other than pain. Patients report their past-month behavior on a five-point Likert scale ($\alpha = 0.86$).

Overdose Risk Behaviors. We have adapted items on overdose risk (ORB) from Strang and colleagues²⁶ by adding risk factors specific to OAs.^{12,18,33,83} This measure was developed with a national consortium of experts. Items include: high dose (more than 100 MEM/day); combining OAs with other substances; route of use; using alone; and returning to usual dose after a period of abstinence. In our pilot RCT, this measure was able to detect substantial between-subject variation, with participants reporting between 0 and 10 behaviors, 70% reporting at least one risk behavior, and a mean number of behaviors of 1.9 (S.D.=2.0).

Secondary Outcomes.

Non-Fatal Overdose Experiences: Established items will be used to assess non-fatal overdose (OESWA and OESWD).⁸⁴ For each overdose, we will assess the date, substances involved, intent (categories including “suicide attempt,” “did not want to die but did not care about the risks,” “accident, effect of drug was not expected,” and “unsure”), preceding events, and actions taken by others.

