Demographics Information on participants' race, gender, sexual orientation, OEF/OIF/OND status (MSI), marital status, employment status, income, and education will be collected. Contact information and housing status, address, phone number, e-mail (if applicable) and type of living arrangement will also be collected.

Analysis plan. The project's data management and analysis will be supervised by [name], who received advanced biostatistics training during her Ph.D. in public health. Tests for linearity, independence, missingness, and distributional assumptions will be conducted on key variables. Distributions will guide modeling decisions and normalizing transformations will be used when appropriate.

Although we expect that randomization will balance the groups, we will validate randomization by comparing groups on key variables potentially related to outcomes. If we identify significant group differences, we will adjust for these variables in models. The EUC condition will be designed to be equal-attention, but we will examine potential associations of the outcomes with length of session in sensitivity models.

Mixed effects regression models (described below) will allow the use of data from all participants, including those with incomplete follow-up, and provides unbiased parameter estimates under the missing-at-random assumption.¹⁰² If the missing-at-random assumption is untenable, we will handle missing data with a pattern mixture model. Where we have missing data on individual variables for more than 15% of observations, we will impute using SAS PROC MI and PROC MIANALYZE to combine the results of PROC MI.

Generalized linear models (GLMs) and generalized linear mixed-effects models (GLMMs). We will assess treatment effects by using GLMs to examine differences between the intervention and EUC groups at specific assessment waves and GLMMs to examine the primary dependent measures over the study period as a whole. GLMMs have the advantage of: 1) adjusting variances for correlated data (i.e., repeated measures); 2) allowing time-varying independent variables; and 3) allowing subject-specific inferences. The link function for GLMs and GLMMs will be based on the distribution for each outcome. We will use procedures SAS PROC MIXED for continuous variables and PROC GLIMMIX for dichotomous and count data.

Aim-specific analyses. All hypotheses will be planned a priori. All analyses will use two-sided tests.

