Aim 1 analyses. Hypothesis 1: Participants randomized to the intervention condition will report fewer overdose risk behaviors than EUC participants at follow-up. The overdose risk behavior is conceptually a composite count of number of behaviors. However, prior to initiating modeling, we will examine the distribution of responses to individual items on the overdose risk behavior assessment as well as the distribution of the overall composite count. Primary analyses will consist of GLMs to examine group (Intervention vs. EUC) as the primary independent variable at each time point and a GLMM to examine the average effect of the intervention over all assessments. If GLM findings suggest that the impact of the intervention may vary by assessment period, this will be examined using a time by group interaction term.

Aim 2 analyses. Hypothesis 2a: Participants randomized to the intervention condition will have lower average MEM/day doses and MPRs than EUC participants over follow-up. Hypothesis 2b: Participants randomized to the intervention condition will report lower levels of aberrant OA use than EUC participants over follow-up. Aim 2 dependent variables will include both objective measures based on pharmacy data and self-reported aberrant use. Prescribed OA dose will reflect escalating doses (likely due to patient request) and high total doses after combining regularly scheduled and "as needed" OAs.¹² An MPR⁸² greater than 1 identifies potential overuse based whether new fills frequently occur before the days supplied by a prior fill have elapsed. The distribution of the daily dose, MPR, and COMM scores will be examined to select appropriate models. The same analysis strategy used to test intervention effects in GLMs and GLMMs for Aim 1 will be used for the dependent variables in Aim 2.

Secondary aim 1 analyses. Hypothesis 3: Participants randomized to the intervention condition will have fewer non-fatal overdoses, fewer injuries and other OA-related adverse events, and better OA storage and disposal behaviors and better functioning than EUC participants. Analysis will follow the general GLM and GLMM framework used in the Aims 1 and 2 analyses, but a survival analysis approach using Cox proportional hazards regression modeling will also be used to examine time-to-event data (non-fatal overdoses and emergency department visits).

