Power analysis. All power analyses are conservative because they are based on a retention rate of 80%, n=360 (180 per condition), despite the fact that the methods will maximize analytic sample size by including individuals with partial follow-up data. All power calculations were based on two-sided tests with $\alpha=0.05$ and were conducted using G*Power software. We estimated power for GLMs for both count and continuous outcomes. For continuous outcomes, such as OA dose and aberrant use (Aim 2), 80% power is achieved to detect a standardized effect size of 0.30. For overdose risk behaviors (Aim 1), we assumed a Poisson distribution and a mean count of 1.9 (based on our pilot work) and found 80% power is achieved to detect an incidence rate ratio of 0.80 for the intervention compared to EUC. We extrapolate from the power calculations presented here for GLMs that power for outcomes in GLMMs will allow for detection of similar effect sizes. Thus, the proposed study has sufficient sample size to detect small to moderate effects.

DISSEMINATION PLAN

Several dissemination products will be developed during this study. We will finalize the intervention training manual and develop additional materials. We will create a video demonstration of the different components of the intervention, with multiple examples for each component in order to show how the intervention is tailored. These products and the computer aid will be shared with key central office stakeholders and made available to VHA clinicians. Additionally, these products will be ready to be used in a future hybrid type-1 implementation study using a stepped wedge design and informed by the Replicating Effective Programs model.¹⁰⁴ This study could examine factors that facilitate implementation as well as fatal and non-fatal overdose as an outcome by implementing the intervention with larger numbers of patients.

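### Secondary event counts (injuries, overdoses, ED visits) are reported since the last assessment, but the count models name no exposure term, so arm-differential missed visits would bias the rate ratio

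*Combined protocol and SAP*

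**What the plan says.** All references are to the combined protocol and SAP.

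- **Recall window** (*Measures*): as a general rule, "the baseline survey will assess past year or lifetime while the follow-up assessments will assess the period since the last assessment".
- **Schedule** (*Data collection procedures*): follow-up at 3, 6 and 12 months. The same section expects about 80% to be interviewed at follow-up.
- **Models** (*Analysis plan*): GLMs by wave and GLMMs across waves. "The link function for GLMs and GLMMs will be based on the distribution for each outcome". Participants with incomplete follow-up stay in the models under a missing-at-random assumption.
- **Pooled effect** (*Aim 1 analyses*): the plan adds "a GLMM to examine the average effect of the intervention over all assessments". Time enters only as a conditional time-by-group interaction.
- **Event outcomes** (*Secondary aim 1 analyses*): non-fatal overdoses, injuries and other adverse events follow the same GLM/GLMM framework. Cox regression is added for overdoses and ED visits.

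No section names an offset, person-time or a window-length term, or says what period a survey covers after a missed visit.

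**The concern.** A missing-at-random argument deals with the record that is absent. It does not deal with the next record, which is observed but covers a longer period. Someone who skips month 3 and attends month 6 reports six months of injuries or ED visits in a record that the model treats like a three-month record. A mixed model does not correct this.

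The extra events fall in whichever arm has more skipped visits. If attendance differs by arm, part of that difference appears as a treatment effect, or hides one, in the secondary safety comparisons.

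**Working it through.** **The plan's own figure.** The only count calculation in the plan is for ORB, where the team "found 80% power is achieved to detect an incidence rate ratio of 0.80 for the intervention compared to EUC". Inputs (*Power analysis*): Poisson mean 1.9, 180 per arm, two-sided 0.05.
- Intervention mean: 1.9 × 0.80 = 1.52.
- SE of the log ratio: √(1/(180 × 1.9) + 1/(180 × 1.52)) = √(0.00292 + 0.00365) = 0.081.
- |ln 0.80| / SE = 0.223 / 0.081 = 2.75, and 2.75 − 1.96 = 0.79, so power is about 0.79.

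The stated 80% reproduces. The mean of 1.9 has no exposure time attached, and this point does not alter the figure.

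**Inputs for the event counts**
- Windows of 3, 3 and 6 months, from the visit schedule.
- Last assessment is read as last *completed* assessment. This is the natural reading, but the text does not define it.
- ED rate of 1.5 visits a year, the figure that *Background* cites for Medicare patients on opioids for chronic pain: 0.375 per 3 months and 0.75 per 6 months.
- 180 per arm analysed.
- *Assumption:* m, the share of those seen at a wave who missed the wave before. The plan's 80% retention does not determine m, since dropouts who never return create no long windows.

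**Expected bias, true ratio 1.** A missed month 3 doubles the month-6 window (6/3), so the mean count rises by the factor 1 + m. A missed month 6 lengthens the month-12 window by half (9/6), so it rises by 1 + 0.5m. The apparent ratio, for the arm with more missed visits over the other, is:

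| Assumed m | Month 6 | Month 12 |
|---|---|---|
| 20% vs 20% | 1.20/1.20 = 1.00 | 1.10/1.10 = 1.00 |
| 22% vs 18% | 1.22/1.18 = 1.03 | 1.11/1.09 = 1.02 |
| 25% vs 15% | 1.25/1.15 = 1.09 | 1.125/1.075 = 1.05 |
| 30% vs 10% | 1.30/1.10 = 1.18 | 1.15/1.05 = 1.10 |

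These ratios do not depend on the event rate, so they apply equally to injuries, for which the plan gives no rate. Month 3 has no earlier follow-up visit to miss and is unaffected.

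**Type I error, by simulation.** Null ED-visit counts, gamma-Poisson with assumed shape 1, quasi-Poisson test. Ranges show the spread over repeat runs.
- 22% vs 18%: about 5% at month 12.
- 25% vs 15%: ratio 1.04 to 1.05 and error about 6% at month 12; 1.08 to 1.09 and 7 to 8% at month 6.
- 30% vs 10%: ratio 1.10 and 9 to 10% at month 12; 1.18 to 1.19 and 12.5 to 15% at month 6.
- With a log-time offset: ratio about 1.00 and error 5 to 6%.

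**ORB, for contrast.** ORB counts distinct behaviors. As an illustration, take 10 items at 19% each (mean 1.9).
- If every behavior is episodic, doubling the window gives 10 × (1 − 0.81²) = 3.44, a factor of 1.81. At 25% vs 15% the month-6 null ratio is (1 + 0.25 × 0.81)/(1 + 0.15 × 0.81) = 1.2025/1.1215 = 1.07.
- If every behavior is persistent, the factor is 1 and the ratio is 1.00.
- An offset applied to persistent behaviors would itself create a ratio of 1.15/1.25 = 0.92.

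**The case against.** **Differential attendance is assumed.** The plan has an equal-attention control meant to keep participants blind, a blinded follow-up assessor, and phone, mail and community options for follow-up. Nothing in it predicts more missed visits in one arm. This stands: the bias is conditional, and the rates above are illustrative.

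**There are safeguards.** Overdoses and ED visits are collected with dates and also analysed by Cox regression, and VHA service use is extracted from records whether or not surveys are completed. This stands in part. The Cox models are additional to the count models, and neither they nor any dating of events is described for injuries.

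**The rule is hedged.** It is stated as a general one, and the window after a missed visit is inferred. That is fair, and is itself a reason to define the window.

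**Stronger readings that the documents do not support.**
- A reader might infer that the Aim 1 result is biased. ORB need not grow with the window, and the share of episodic behaviors is unknown. Nor can the ORB mean of 1.9 be used as an event rate that accrues with time.
- A reader might infer that the 3/3/6-month spacing alone biases the comparison. Each wave's nominal window is common to both arms: the intercept absorbs it in the wave-specific GLMs, and in a log-link GLMM it leaves the group ratio unbiased. Any loss of precision is trivial.
- Other Aim 2 outcomes are outside the point. COMM uses a past-month window, and dose and MPR come chiefly from pharmacy records.

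**Conclusion.** The point holds for the secondary event counts: injuries above all, and the GLM/GLMM analyses of overdoses and ED visits. With equal missed visits there is no bias. With a ten-point difference between arms (25% vs 15%) the spurious effect is about 4 to 5% at month 12 and 8 to 9% at month 6, with little rise in type I error. It becomes material only with larger imbalance, such as 30% vs 10%.

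These sizes rest on assumed missed-visit rates, the natural reading of the recall rule and a constant event rate. The type I error figures also rest on the assumed ED-visit rate and dispersion. The primary conclusions are not shown to be at risk. The change is still worth making, because attendance by arm cannot be known in advance and the remedy is nearly free.

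**What to change.** - State what period a survey covers after a missed visit.
- In the GLMs and GLMMs for overdoses, ED visits and injuries, use log(days since last completed assessment) as an offset. For overdoses and ED visits, the collected event dates could instead be used to assign events to fixed intervals.
- Include assessment wave as a fixed effect in the GLMMs.
- For ORB, do not use an offset. At most, report a sensitivity analysis restricted to records with the nominal window. It is a sensitivity analysis only, because the restriction conditions on attendance after randomization.

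**Cost.** Plan wording, with no new visits, participants or instruments. Assessment completion dates must be kept in the analysis file; the documents mention only due dates. The offset assumes a constant event rate within each window, and it does not repair missingness that is related to the outcome.

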Aim 1) to examine if patients randomly assigned to a brief overdose prevention intervention report reduced overdose risk behaviors (e.g., higher dose, concurrent alcohol use, concurrent other drug/medication use, returning to normal dose after breaks in use) over one year of follow-up compared to patients assigned to equal attention EUC.

Aim 2) to examine if patients randomly assigned to a brief overdose prevention intervention have lower total quantities of opioids prescribed (from pharmacy fill records) and aberrant opioid use (e.g., using for reasons other than pain, obtaining opioids from someone other than primary provider) over one year of follow-up compared to patients assigned to equal attention EUC.

The study will include two **secondary aims**: **1)** to examine if patients randomly assigned to the brief intervention have fewer non-fatal overdoses and other medication-related adverse events (emergency department visits, over-sedation, injuries), better functioning, and more often store and dispose of opioids safely compared to patients assigned to EUC; and **2)** to examine mediators (motivation and self-efficacy) and moderators (OIF/OEF/OND status, baseline mental health) of intervention effects.

The proposed POST study will increase our understanding of strategies to reduce adverse outcomes related to prescription opioid use, namely, risk of overdose, among VHA primary care patients. This study is the next logical step in addressing the risks of prescription opioid use among VHA patients, providing critical, initial data to inform VHA clinicians to prevent adverse opioid-related outcomes. Knowledge generated from

this pragmatic trial is likely to have broad implications for improving safe opioid use, the enhancement of PC-MHI services, and the quality of pain care for current and future VHA patients.

BACKGROUND

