Treatment Use (including ED): Use of specific types of clinical services will be assessed with questions adapted from the Treatment Service Review (TSR).⁸⁵ For ED use, participants will be asked “how many times did you visit an emergency room?” and asked what were the problems for which they were seeking treatment and the date of each visit. Parallel questions will assess non-VHA use of addictions, pain, and mental health services. We will assess alternative pain treatment (AT) modalities utilized during baseline and a more extensive list of pain treatments and self-management strategies during follow-up assessments.

Injuries: The Revised Injury Behavior Checklist (RIBC) for adults⁸⁶ will be used to identify 4 types of injuries, including those not resulting in use of ED services (overdose will be excluded from this measure).

Over-sedation: Pain Treatment Satisfaction Scale (PTSS)⁸⁷ is a 12-item tool designed to assess the OA-related side effects on a scale of 0 (“Did not experience” to 5 (“Extremely bothered”). Over-sedation will be measured as “Excessive fatigue”, “inability to concentrate”, and/or “drowsiness.”

Safe Storage and Disposal of OAs: We will adapt items by McCauley and colleagues⁸⁸ designed to assess knowledge of safe storage and disposal of OAs. This measure is sensitive to the effects of a web-based psychoeducation on safe OA storage and disposal.

Functioning: We will use the first item from the Veterans RAND 12-item Healthy Survey (VR-12)⁸⁹. In the interest of reducing patient burden, we will use the single item. This is consistent with health status items

used in many national health studies^{90, 91}.

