Secondary Aim 2 analyses. Hypothesis 4a: The effect of the intervention on overdose risk behaviors and OA use will be mediated by post-intervention self-efficacy and motivation to change. Hypothesis 4b: OIF/OEF/OND status and baseline psychiatric distress will moderate the effect of the intervention on overdose risk behaviors and OA use. Mediators: In further analysis of the GLMs and GLMMs developed for Aims 1 and

2, we will include potential mediators in additional models and examine changes in effect size for the group indicator. Following the recommendations of Preacher and Kelley¹⁰³, we will use a κ^2 statistic to estimate the effect size and conduct significant testing of the mediation. *Moderators*: An interaction effect between each hypothesized moderator and the group indicator (intervention vs. EUC) will be specified in separate GLMs. For longitudinal analysis, we will examine baseline moderator by group interactions in GLMMs.

Additional analyses. We will examine descriptive statistics of the “perceived satisfaction and utility” measure from the post-test for further refinement of the intervention materials for follow-up. Descriptive statistics will also be used to examine differences between those who participated and those who refused participation of select characteristics. The focus group interviews conducted with prescribers will be entered into NVivo 10. [name] and the coordinator will independently read transcripts and use an iterative process to develop a coding scheme. Final codes will be grouped conceptually into meaningful themes and sub-themes. We will also calculate the number needed to treat to prevent one adverse event and amount of therapist time needed to prevent one adverse event.

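### Over-sedation (secondary outcome) has no severity level or combination rule; scored as any one symptom present, it ignores severity and, under assumed item prevalences of 30–60%, has about 50–77% power where the summed score has about 81%

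*Combined protocol and SAP*

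**What the plan says.** The Secondary Outcomes part of the Measures section takes over-sedation from a side-effect questionnaire described as "designed to assess the OA-related side effects on a scale of 0 (“Did not experience” to 5 (“Extremely bothered". The definition is one sentence: "Over-sedation will be measured as “Excessive fatigue”, “inability to concentrate”, and/or “drowsiness". No score is named that counts as over-sedation, and nothing says whether the outcome is a yes/no variable, a count of symptoms or a score.

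The first secondary aim lists over-sedation among "other medication-related adverse events (emergency department visits, over-sedation, injuries", and Hypothesis 3 predicts fewer such events in the intervention arm. For that aim, "Analysis will follow the general GLM and GLMM framework used in the Aims 1 and 2 analyses", with Cox regression added for "time-to-event data (non-fatal overdoses and emergency department visits". Over-sedation is not in the Cox list. The general modelling text says "The link function for GLMs and GLMMs will be based on the distribution for each outcome". Under Additional analyses the plan will also calculate the "number needed to treat to prevent one adverse event", without saying which event is meant.

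The table of measures shows the questionnaire collected at baseline and at the follow-ups.

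**The concern.** Items joined by and/or describe the presence of at least one symptom; they do not describe a sum or a mean. The outcome is also listed with emergency visits and injuries as an adverse event, and the only symptom-free anchor on the scale is 0. The reading closest to hand is therefore that a score above 0 on any item makes a case.

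Scored that way, the outcome ignores how much the symptoms bother the patient, although the questionnaire records it. It responds only when a patient moves between no symptoms at all and some symptom. An intervention that made drowsiness milder without abolishing it would leave the indicator unchanged.

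The opposite reading, all three symptoms required, gives a very different outcome. Since the link function is chosen from the distribution of an outcome that is not yet scored, both the scoring and the model could be settled after the data are seen.

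**Working it through.** **Inputs from the plan.** 180 per arm after 80% retention, two-sided alpha 0.05, and a standardized effect of 0.30 for continuous outcomes (Power analysis). The plan gives no prevalence, effect size or power for over-sedation.

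**The plan's own figure.** Power for two means = Φ(d·√(n/2) − 1.96) = Φ(0.30 × √90 − 1.96) = Φ(2.846 − 1.960) = Φ(0.886) = 81%. The stated 80% reproduces. It is also the power of any over-sedation score on which the effect is 0.30 SD.

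**What the any-of-three rule does, without assumptions.** Let the indicator be 1 if the largest of the three scores is at least 1.
- (1, 0, 0) gives 1, with sum 1.
- (5, 5, 5) gives 1, with sum 15.
- (5, 5, 5) falling to (1, 1, 1) stays at 1, while the sum falls from 15 to 3.

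**Size under assumed prevalences.** Let q be the proportion scoring above 0 on one item, taken as equal for the three. If the items were independent, any-of-three prevalence would be 1 − (1 − q)³; if fully dependent, it would be q. For q = 50% that is 87.5% and 50%. To work between these limits, assume three normal latent items with correlation 0.4 or 0.6, cut into 0–5 scores at points 0.4 SD apart, the lowest placed so that a proportion q score above 0. Shift the treated arm by the amount that gives exactly 0.30 SD on the 0–15 sum, so the sum has 81% power in every row.

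Power for the indicator uses p̄ = (p₀ + p₁)/2 and Φ((|p₀ − p₁| − 1.96·√(2p̄(1 − p̄)/n)) / √((p₀(1 − p₀) + p₁(1 − p₁))/n)). For example, at q = 50% and correlation 0.4 the shift takes any-of-three from 77.7% to 67.6%. Power is Φ((0.101 − 1.96 × 0.0470)/0.0467) = Φ(0.19) = 58%.

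| Item prevalence q (assumed) | Any-of-three prevalence, control (corr. 0.4 / 0.6) | Power, any-of-three (corr. 0.4 / 0.6) | Power, sum |
|---|---|---|---|
| 20% | 41% / 37% | 79% / 83% | 81% |
| 30% | 56% / 50% | 73% / 77% | 81% |
| 40% | 68% / 62% | 66% / 72% | 81% |
| 50% | 78% / 72% | 58% / 64% | 81% |
| 60% | 86% / 81% | 48% / 56% | 81% |
| 80% | 96% / 94% | 26% / 34% | 81% |

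Spacing the cuts 0.5 SD apart changes these powers by less than one percentage point. Requiring all three symptoms would label only 8–38% of patients for q = 30–60%, so the choice of reading alone changes what the outcome is.

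**The case against.** The strongest reply is that the criticised rule is not in the text. The plan nowhere says that a score above 0 is an event, over-sedation is not among the outcomes sent to Cox regression, and the modelling section provides for continuous outcomes. A graded analysis is already allowed. This stands: the defect is an open rule, and any-of-three is its most natural reading, not a written instruction.

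A reader might go further and infer that slight fatigue alone will be counted as over-sedation, that prevalence will sit near its ceiling, and that real improvement will go unseen. The documents support none of these as fact. The fatigue item is worded as excessive fatigue and the scale rates bother, so a score of 1 means excessive fatigue with little bother. No item prevalence is given, and for assumed item prevalences of 30–60% the indicator covers about 50–86% of patients, much of which is not close to a ceiling. At 20% the indicator does about as well as the sum.

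Nor does the plan say that over-sedation will enter the number needed to treat. It is a candidate only because the event there is undefined.

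Finally, fatigue and poor concentration make up two thirds of a three-item sum, and neither is specific to sedation. That is a fair limit on what the score means, but it applies equally to the plan's own choice of items.

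**Conclusion.** The point holds as a specification gap with a conditional cost. What is certain from the text is that over-sedation has no severity level, combination rule or outcome type, and that the most natural reading treats (1, 0, 0) and (5, 5, 5) alike.

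The size rests on assumptions. With 30–60% of patients endorsing each item, correlation 0.4–0.6, 180 per arm and 0.30 SD on the sum, power is about 81% for the sum and about 50–77% for the any-of-three indicator (48% at the lowest corner). With items at about 20% there is little or no loss; with items at 80% the indicator keeps only about a quarter to a third. These figures assume equal item prevalences and the same latent shift on each item.

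This is one component of a secondary aim, so the conclusions on overdose risk behaviors, prescribed dose and aberrant use do not depend on it. It is worth correcting because the remedy is nearly free.

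**What to change.** Replace the and/or sentence with a single scoring rule: the sum of the three items (0–15), or equivalently their mean, compared between arms in the planned GLM and GLMM with the baseline score as covariate. As written, the plan adjusts only for variables on which the arms differ significantly, so the baseline covariate should be named.

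Keep over-sedation out of the number needed to treat unless one yes/no definition with a stated cut-point is fixed before unblinding. A higher cut-point is not automatically better: if the symptoms are uncommon, it lowers power.

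The cost is one or two sentences of analysis-plan wording, because the items are already collected at baseline and follow-up. The downside is that the main over-sedation result becomes a mean difference on a symptom score instead of a proportion of patients affected.
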